### 7.2.2 Exclusion Criteria

Subjects who meet any of the exclusion criteria described below will not be eligible for this clinical investigation.

1. Subjects are unable or unwilling to comply with the requirements of the study as determined by the investigator.
2. Investigator site personnel directly affiliated with this study and/or their immediate families; immediate family is defined as a spouse, parent, child, or sibling.
3. Cochlear employees or employees of Contract Research Organizations or contractors engaged by Cochlear for the purposes of this study.

### 7.2.3 Number of Subjects Required

200 subjects will be enrolled in the clinical investigation, with a maximum estimated overhead of 10% taking into consideration the simultaneous recruitment at all sites. It is estimated that approximately double the size will need to be screened (30) to meet this sample size. Additionally, to meet the

validation requirements on the COMOT-15, a minimum of 30 subjects (29) with complete data are required at both the Spanish and French clinics (see section 7.3.2.1 for detailed justification).

## 7.2.4 Vulnerable Populations

Not applicable.

## 7.2.5 Recruitment and Study Duration

The following subject status definitions apply:

- Enrolled: A subject that has signed the Informed Consent Form (ICF) for the study.
- Screen Fail: An Enrolled subject that has been determined to not meet one or more eligibility criteria.
- Participated: Subjects who have met eligibility criteria and have started on protocol defined events.
- Withdrawn: An Enrolled subject who withdrew or was withdrawn by the Investigator or Sponsor before the expected End of Study.
- Completed: Enrolled subjects who complete the required tasks and schedule.

The recruitment period for the clinical investigation is estimated to be approximately 12 months from the time of first subject enrolled to the last subject.

Recruitment of subjects shall be performed in a back-chronological order from the primary tympanoplasty surgery. Recruitment shall start with the last subject that has undergone this procedure in the year 2016 and chronologically working backwards until recruitment targets are met. This process will avoid any recruitment bias.

The expected duration of each subject's participation in the clinical investigation is the time it takes for the subject to complete and return the ICF, questionnaires and survey. Time for completing the questionnaires is estimated to 30-40 minutes.

Clinical Investigation completion is defined as the recording and completion of the last medical record search for the last enrolled subject in the electronic Case Report Forms (eCRF).

## 7.2.6 Criteria for Subject Withdrawal

Subjects can decide to withdraw from the investigation at any time. The Investigator shall ask the reason(s). The reason for withdrawal (if available) should be documented in the subject's source files and the referent electronic case report form (eCRF).

The Investigator or Sponsor may also decide to withdraw a subject from the clinical investigation if it is considered to be in the subject's best interests.

Subject withdrawal may be for any of the following reasons:

- CIP or GCP deviation
- Subject withdrew consent
- Subject died

- Sponsor decision
- Investigator decision
- Other (specify)

If a subject is lost to follow-up, every possible effort must be made by the study site personnel to contact the subject and determine the reason for discontinuation. At least 3 separate attempts taken to contact the subject must be documented.

Participating subjects who are withdrawn/discontinued will be replaced if medical record search is not completed.

## **7.2.7 Randomisation Procedures**

Not applicable.

### **7.2.7.1 Blinding Procedures**

Not applicable.

## **7.2.8 Post-investigation Medical Care**

No specific care will be provided for the subjects after this study has been completed.

## **7.3 Performance Evaluations and Procedures**

### **7.3.1 Eligibility evaluations and Procedures**

Screening of subjects include searches by site personnel in medical records for inclusion and exclusion criteria.

The search for a primary tympanoplasty to improve hearing can include any primary tympanoplasty of types I-V based on the Wullstein classification (31).

Eligible subjects will be included chronologically based on date of primary tympanoplasty, from most recent to least recent. In a first draw, the number of subjects intended to be enrolled at a site plus 20% (to account for non-responders) will be contacted. To confirm that subjects are alive before they are contacted, a search in public death records should be performed according to local regulations and practices.

Subjects will first be contacted via mail or by phone. If they agree to receive a consent form, this will either be sent to them by mail or shared directly at the clinic if they are scheduled for an appointment. The subject has the right to have sufficient time to read the consent, ask questions and have those questions answered by the site personnel responsible for consent. When the consent form is signed by the subject at home, it will be sent back to the clinic by registered mail using a pre-filled and stamped envelope with the address of the clinic. The date of the consent discussion will be documented in the informed consent form and once this is signed by the responsible site staff, a copy of the mutually signed form will be shared with the subject.

If the number of targeted subjects at the clinic is not reached in a first draw, a second and potential third draws (in the same way as the first one) will be performed until the targeted number of subjects for the site is reached.

## 7.3.2 Participant Evaluations and Procedures

### 7.3.2.1 Study data – Questionnaires/survey

When a subject is enrolled in the investigation, data collection can start. In case subjects are due for a follow-up appointment at the clinic, as per standard of care, questionnaires and survey can be completed at site. For those subjects where an aided (unaided if no hearing aid used) audiogram between 2018 and point of enrolment is available, and who are not scheduled to any appointment at the clinic during the investigation period, questionnaires and survey (together with a copy of the mutual signed ICF) are sent via mail to be completed at home. All questions regarding the questionnaires and survey can be raised with the site personnel. If completed at home, questionnaires and survey shall be sent back to the clinic by registered mail using a pre-filled and stamped envelope with the address of the clinic.

The completeness of the questionnaires and survey will be verified by site personnel. Incomplete data will be followed-up with the subject, if answered at home by sending a copy of the questionnaire/survey back to the subject where incomplete parts requiring an answer are highlighted. If the questionnaires and survey are not returned; every possible effort must be made by the study site personnel to contact the subject and determine the reason for discontinuation. At least 3 separate attempts taken to contact the subject must be documented.

The subjects will be asked to complete the following survey and questionnaires:

- Health care utilisation survey (adapted version of Client Service Receipt Inventory, CSRI)
- Health-Related Quality of Life – Health Utilities Index Mark 3 (HUI3)
- Chronic Otitis Media Outcome Test-15 (COMOT-15)
- Speech, Spatial and Qualities of Hearing Scale (SSQ-12 version)

#### Health care utilisation survey

The Adapted version of the Client Service Receipt Inventory (CSRI) (32), is a research instrument developed in the mid-1980s to collect information on primarily service utilisation and has been used in over 500 studies.

The CSRI can be used at multiple points within a study, thus tracking changes over time. The CSRI is also adaptable in administration. Although originally designed to be administered to the service user or their carer face to face with a trained interviewer, the CSRI has been successfully administered via post for the service user to be completed by themselves.

The adapted version of CSRI will, in this investigation, collect data referring to the 6 months before enrolment regarding demographics (marital status, cohabitation, usual place of residence, education level), medical history (chronic diseases, smoking status, date when first diagnosed with chronic ear infection, current middle ear issues, recurrent ear infections), hearing rehabilitation (current hearing aid or hearing device and category of hearing aid/device and hours per day of usage if applicable), health care utilisation related to ear infection and hearing difficulties (number of face-to-face consultations with care providers, investigations or diagnostic tests, number of in-patient admissions, medications) and employment information (employment status, inability to work in days/hours).

#### Health-Related Quality of Life – Health Utilities Index Mark III (HUI3)

HUI® is a generic preference-based system for measuring comprehensive health status and Health-Related Quality of Life (HRQoL) (33). HUI provides descriptive evidence on multiple dimensions of health status, a score for each dimension of health and an overall HRQoL score. The scoring systems provide utility (preference) scores on a generic scale where dead = 0.00 and perfect health = 1.00. HUI3 will be used in this study. The HUI3 classification system is comprised of 8 attributes: Vision, Hearing, Speech, Ambulation, Dexterity, Emotion, Cognition and Pain – each with 5 or 6 levels of ability/disability (34). The version in this clinical study uses a recall time of 1 week.

The license to use the HUI questionnaire is purchased from Health Utilities Inc., [name].

#### Speech, Spatial and Qualities of Hearing Scale (SSQ-12 version)

The Speech, Spatial, and Qualities of Hearing Scale questionnaire (SSQ-12) (35) was developed in the MRC Institute of Hearing Research, UK, and is a scaled-down version of the 49 items SSQ questionnaire (36). It is designed to compile a sub-set of items from the longer original 49 version to represent the scale as a whole, measuring self-reported auditory disability, reflecting the reality of hearing in the everyday world. It has been shown to provide similar results to SSQ-49 (35). It covers:

- Hearing speech in a variety of competing contexts
- The directional, distance and movement components of spatial hearing
- Segregation of sounds and attending to simultaneous speech streams
- Ease of listening
- The naturalness, clarity and identifiability of different speakers, different musical pieces and instruments, and different everyday sounds

#### Chronic Otitis Media Outcome Test-15 (COMOT-15) and validation in French and Spanish

The subjects will be asked to complete a Chronic Otitis Media Outcome Test-15 (37).

COMOT-15 is 15-item questionnaire that is a reliable and sensitive instrument for measurement of HR-QoL of subjects with COM.

The instrument consists of three subscales: ear symptoms (questions 1-6), hearing function (questions 7-9), and mental health (questions 10-13), which form the overall score (questions 1-13). In addition, one question on the general evaluation of the impact of COM on QoL (question 14) and one question to indicate the frequency of doctor visits in the last six months as a result of COM (question 15) are asked. The total score and the sub-scores are transformed to a 0-100 scale by dividing the sum of the raw scores of the items by the sum of spans of the items followed by multiplying by 100. Overall scores and sub-scores will be calculated for subjects based on this methodology, and compared between interventions, if feasible. COMOT-15 is validated in German and will be used in its original version at German-speaking clinics. For non-German speaking clinics, the COMOT-15 has been cross-translated and linguistically validated in Spanish and French by a certified translation agency (Software and Documentation Localization PLC) using published methodology (38). As the COMOT-15 is a COM-specific questionnaire that has already demonstrated reliability in additional languages, validation of the instrument in French and Spanish will require that

the questionnaire is completed by a minimum of 30 subjects per language, based on the accepted subject to item ratio of at least 2 (29). These subjects must have an accompanying audiogram (PTA4 at minimum) collected within 12 months of questionnaire completeness and completed the SSQ and HUI3 questionnaire as part of the investigation. Aided audiograms should be collected if the subject is using a hearing device. The widely accepted Cronbach's alpha value of 0.7 will be used as a cut-off to measure consistency.

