### 7.1.1 Design Rationale

This study is designed to collect information regarding health care interventions that follow a primary tympanoplasty with residual hearing loss among adult subjects with diagnosis of COM, with or without cholesteatoma. A multicentre set-up is necessary to accurately capture the standard of care as this can vary at each site, as determined by treatment practice surveys at potential sites and it is important that we capture outcomes on all potential interventions that may be offered as part of standard care. The rationale to collect information from subjects who underwent a primary tympanoplasty procedure between 2010-2016 is to increase the likelihood of availability of electronic medical records data as these systems have only typically been introduced in recent years. This inclusion time frame is also important to capture the current standard of care rather than outcomes from obsolete procedures and to find enough subjects that have at least five years follow-up data so that we may capture patients who have reached a steady state. Subjects with single-sided deafness are not eligible for the study as COM with or without cholesteatoma leads to mainly conductive or mixed hearing loss. Paediatric subjects are excluded from the study as tympanoplasties are delayed until adulthood in some clinics.

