# 9 STATISTICAL CONSIDERATIONS

## 9.1 General Considerations

Descriptive statistics will be used for analysis in this study. All analyses will be made on the full data set. All analyses will be presented as aggregated data without the possibility of identifying data from individual subjects.

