### Patient reported outcome

Attribute levels and scores will be calculated for individual subscales and general scores for each subject. If possible, data will also be grouped by intervention type and differences in scores between these groups will be analysed. Change in score will be assessed using the Wilcoxon rank sum test and sub-group analyses by age and gender may be performed, if feasible.

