### Validation of COMOT-15 in French and Spanish

The validated German version of the COMOT-15 that has been translated, back translated and linguistically validated will be used to validate the instruments reliability in French and Spanish. The instrument will be administered according to the original procedure and criterion validity will be assessed by comparing COMOT-15 scores with PTA4. COMOT-15 properties, including internal consistency will be assessed using Cronbach's alpha, where a value of >0.7 is indicative of acceptable reliability for clinical purposes.

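### The between-intervention COMOT-15 comparison is not stratified by language, so a score offset between the German, French and Spanish versions would be confounded with intervention wherever treatment mix differs by country

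*Combined protocol and SAP*

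**What the plan says.** The COMOT-15 is one of three questionnaires under the secondary endpoints (Section 9.2.2). Section 7.3.2.1 plans its use as follows: "Overall scores and sub-scores will be calculated for subjects based on this methodology, and compared between interventions, if feasible". Section 9.7 (Patient reported outcome) adds that, if possible, "data will also be grouped by intervention type and differences in scores between these groups will be analysed". It names the Wilcoxon rank sum test and mentions only age and gender as possible subgroups. That sentence speaks of a change in score, but the questionnaires are collected once, at enrolment, so I read it as the test between intervention groups.

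On the versions, Section 7.3.2.1 says: "COMOT-15 is validated in German and will be used in its original version at German-speaking clinics". For the other clinics, "the COMOT-15 has been cross-translated and linguistically validated in Spanish and French by a certified translation agency". The psychometric validation of those two versions is an objective of this study. It uses the subjects' own responses, with criterion validity judged against PTA4 and internal consistency by Cronbach's alpha, "where a value of >0.7 is indicative of acceptable reliability for clinical purposes" (Section 9.7).

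On the analysis set, Section 9.1 says: "All analyses will be made on the full data set". Section 9.5 defines that set as everyone enrolled. On treatment patterns, Section 7.1.1 says: "A multicentre set-up is necessary to accurately capture the standard of care as this can vary at each site".

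**The concern.** The version a subject completes follows the clinic, and so the country. If care differs between sites, the interventions being compared may hold different proportions of German, French and Spanish respondents. Suppose scores on one version run systematically higher or lower, through translation, response habits or other country factors. An unstratified test would then attribute part of that offset to the intervention.

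The validation offers no protection here, because both of its planned checks look within a language. The German respondents complete the reference version under the same entry criteria, but Section 9.7 asks for no statistic from them. A low French or Spanish alpha could therefore not be told apart from an effect of this selected population.

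**Working it through.** **1. The plan's own figure.** The validation sample is "a minimum of 30 subjects per language, based on the accepted subject to item ratio of at least 2". The instrument has 15 items, and 15 × 2 = 30. This reproduces.

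**2. How much of the data is involved.** The minimum is 30 French + 30 Spanish = 60 of 200, or 30%. With even recruitment by country (an assumption) it is about two thirds.

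**3. What the planned checks can detect.** Alpha depends only on item variances and the variance of the sum. Adding a constant to the items changes neither: in a 13-item test case alpha was 0.821 before and after a shift. A correlation with PTA4 within one language is unchanged for the same reason. Both checks can therefore pass while an offset remains.

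**4. Bias.** Let d be the offset of the translated versions in SD units, and let p1 and p2 be the shares of non-German respondents in two intervention groups. With no true effect:

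bias = d × (p1 − p2)

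The documents give neither d nor the shares, so I show ranges.
- Smallest case: 0.3 × (0.80 − 0.53) = 0.081 SD.
- Largest case: 0.5 × (0.90 − 0.40) = 0.25 SD.
- Equal mix: 0, whatever d is.

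**5. False-positive rate of the unstratified rank sum test.** Simulation with 4,000 replicates, normal scores, no intervention effect, two-sided 5% level, 100 v 100:

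| Non-German share | d = 0.3 | d = 0.5 |
|---|---|---|
| 80% v 53% | 8.3% | 14.8% |
| 87% v 47% | 12.9% | 27.2% |
| 90% v 40% | 17.8% | 39.3% |

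Hand check of the corners, using a normal test on means:
- The standard error is √(1/100 + 1/100) = 0.141.
- 0.081/0.141 = 0.57, so the rejection rate is Φ(0.57 − 1.96) + Φ(−0.57 − 1.96), about 9%.
- 0.25/0.141 = 1.77 gives about 42%. This is slightly high because it ignores the extra variance from mixing languages and the efficiency of ranks.

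**6. Unequal groups and small mix differences.** The same offsets and shares give:
- 20 v 180: about 6% to 9% (d = 0.3) and about 7% to 17% (d = 0.5).
- 5 v 195: 5% to 6% and 5% to 8%. Section 9.4 puts the rarest intervention at 2.63%, and 200 × 0.0263 = 5.3 subjects.
- 70% v 63% at 100 v 100: about 5% at either offset.

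**7. Language-stratified test.** A separate simulation at 100 v 100 used SD 20 on the 0–100 scale and two strata (German, other). With a 10-point (0.5 SD) offset, the unstratified test rejected in 10.5%, 17.3% and 39.1% of runs for mix differences of 20, 30 and 50 points. The van Elteren test stayed between 4.3% and 5.3% in every scenario.

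**8. Effect of low reliability alone.** If reliability fell from 0.9 to 0.5 in all subjects, a 0.4 SD effect would become 0.4 × √(0.5/0.9) = 0.30 SD. Power at 100 v 100 would fall from 81% to 56%. That is dilution, not a false difference.

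**9. Precision of alpha at the minimum sample.** The Feldt limits are 1 − (1 − alpha) × F, with n − 1 and (n − 1)(k − 1) degrees of freedom. For n = 30, k = 13 and an observed alpha of 0.70, the 95% interval is about 0.51 to 0.84.

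**The case against.** The strongest reply is that much of the worry rests on what the plan leaves unsaid. A reader might infer that French and Spanish scores will be pooled with German ones whatever the validation shows. The documents do not say so. Sections 9.1 and 9.5 define who is analysed, not how versions are merged. Where the plan means to pool across countries, as for unit costs in Section 9.7, it says so. The comparison is also conditional on feasibility. This stands: the supported statement is that no stratum and no consequence of missing 0.7 are specified.

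A reader might also infer that a translation failing on alpha would itself create an intervention difference. It would not: failing that criterion means low reliability, which mainly dilutes differences (step 8). Nor are these untested translations, since Section 7.3.2.1 reports linguistic validation and reliability already shown in further languages.

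The size is assumption-driven. Section 7.1.1 says care varies by site but gives no country pattern, and small intervention groups or small mix differences bring the rate close to 5%. The study is descriptive, with no hypotheses (Section 9.3).

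What survives is the confounding route. The plan names a significance test between intervention groups, gives its own reason to expect treatment to vary by site, and has no design or analysis feature that separates language from intervention. The feasibility wording is tied to neither language nor validation.

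**Conclusion.** The point holds as a weakness in a conditional secondary analysis and should be corrected. An offset between language versions would be confounded with intervention wherever intervention mix differs by country, and the planned validation could not reveal it.

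Under offsets of 0.3 to 0.5 SD and mix differences of 27 to 50 points, the false-positive rate is about 8% to 39% at 100 v 100 and about 6% to 17% at 20 v 180. It is about 5% with equal mix or with a stratified test. Offset, mix and group sizes are all assumptions. The documents support the direction of the risk, not a particular value. They do not support the claim that a failed validation would be ignored or would by itself produce a false intervention effect. The primary endpoint and the sample size are untouched.

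**What to change.** Amend Section 9.7 as follows:

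1. Report COMOT-15 totals and sub-scores by language.
2. Stratify every between-intervention COMOT-15 comparison by language, for example with the van Elteren test. If an intervention occurs in only one language, say that the comparison cannot be separated from language.
3. Compute the same reliability and validity statistics in the German respondents, as a reference for the French and Spanish results.
4. Add a sensitivity analysis that leaves out any language version missing the 0.7 criterion (German only if both miss it).

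Item 4 is preferable to a hard rule that pools only versions passing 0.7. Such a rule could not detect an offset and, with the interval in step 9, would include or drop a version largely by chance at the minimum sample.

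The cost is plan wording, a few extra tables from data already being collected, and a small loss of power from stratification.
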